Low-Intensity Focused Ultrasound Pulsation for Treatment of Motor Deficits in Parkinson's Disease

NCT04593875

October 16, 2022

APPROACH

Participants. Participants will consist of 30 adults, aged 18 to 85 years, diagnosed with Parkinson's Disease (PD).

Subject Recruitment. Subjects will be recruited using flyers and brochures distributed physically and online, as well as from the UCLA Movement Disorder Program in collaboration with [name], MD, PhD. A subpage on the Staglin IMHRO Center for Cognitive Neuroscience (henceforth CCN) website will include study information and an interest form to submit contact information if interested. Recruitment mailers will be distributed to doctor's offices and clinics, where patients (or their doctor's office, upon patient's request) can mail us their contact information if interested in the study.

Screening. Participants will be contacted by study staff who will conduct a telephone screening to ensure eligibility and suitability for MRI.

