fMRI Validated LIFUP stimulation. We will use a Brainsonix ultrasound system with a transducer that fits in the 20-channel head coil. Participants will have the low-intensity focused ultrasound pulsation (LIFUP) transducer approximately aimed at the internal globus pallidus (GPI) using skin surface fiducials and gently strapped in place to their head. To minimize the ultrasound energy's exposure to air, a gel pad will be placed between the transducer and the participant's scalp. Participants will then be placed into the scanner where head scout scans will be used to guide more precise targeting adjustments. Once targeting is complete, a T1 image will verify the position of the LIFUP transducer and allow for estimation of the spatial location of the sonication beam focus (approximately 5mm long x 7mm diameter). Participants will receive active sonication at one visit and sham sonication at the other, the order of which will be randomized and counterbalanced across participants. The sonication protocol will consist of 20 ultrasound sonifications in a 30 s ON, 30 s OFF fashion at 650KHz, $Ispta \leq 720 \text{ mW/cm}^2$, 5% duty cycle, 0.5ms pulse width, 73.15mvP-P amplitude, and 100Hz pulse repetition frequency. For sham sonication, the gel pad will block close to all of the ultrasound energy from the transducer. For active sonication, the gel pad will allow the ultrasound energy to pass through. These gel pads are identical in appearance. Resting state fMRI (rs-fMRI) will be collected simultaneously with LIFUP (or sham) sonication.

MRI Data Acquisition: We will use a 3-Tesla Siemens PRISMA scanner. We will collect high-resolution 0.8 mm^3 T1-weighted images, pseudo-continuous arterial spin labeling (PCASL) images, and rs-fMRI images. Total time in the scanner will be approximately 75 minutes each session.

Analysis and Publications. MRI data analysis will begin immediately during data collection, as structural and functional MRI are used to ensure successful targeting of LIFUP sonication. Group level analysis will occur after data from 30 subjects have been collected.

This project has four main aims:

#1: Validate basal ganglia-thalamocortical (BGTC) network perfusion and resting state functional connectivity (rs-FC) is associated with Parkinson's Disease (PD) deficits in cognition and motor impairments.

#2: Use LIFUP to modulate neural activity in the GPI, and PCASL pre- and post- LIFUP to assess up-regulation of BGTC network perfusion.

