#3: Measure BGTC network rs-FC before, during, and after LIFUP stimulation.

#4: Assess potential LIFUP-related changes in motor function and their association with changes in perfusion and rs-FC.

PROCEDURES

MRI Analysis. Preprocessing and analyses will be performed using FSL Version 6.0 (www.fmrib.ox.ac.uk/fsl). Structural data will be linearly registered to the standard MNI152 T1 2mm brain. Processing of fMRI data will include correcting for motion artifacts (using framewise displacement, DVARS, within-subject independent component analysis, and outlier removal),

slice timing correction, high-pass temporal filtering ($t > 0.01$ Hz) unwarping, and spatial smoothing (Gaussian Kernel FWHM = 8mm). Functional data will be linearly registered to stereotaxic MNI space and co-registered with anatomic data for each participant. Subjects with greater than 0.5mm mean framewise displacement will be excluded from analyses. PCASL scans will be transferred to MNI space using non-linear registration in FSL and then linearly registered with anatomic data for each participant.

Stimulation-related fMRI. rs-fMRI will be collected continuously during the LIFUP stimulation paradigms. A block-design model will be used to statistically compare the blood oxygenation level dependent (BOLD) signal during LIFUP stimulation blocks to the BOLD signal during no-stimulation blocks. To examine LIFUP-related network connectivity, we will use a seed-based approach and examine whole brain connectivity with the LIFUP target of interest⁶⁹ and compare between stimulation (on-off) conditions using psychophysiological interaction modeling (PPI)⁷⁰. We will also use dynamic connectivity to evaluate changes in connectivity across the course of the LIFUP stimulation paradigm.

RS-fMRI. We will compare rs-FC before and after stimulation. Independent component analyses (ICA) will be used to statistically extract functional networks from each participant's rs-fMRI. Dual-regression analysis will then compare resting state networks between baseline and post-LIFUP to determine the effect of LIFUP on resting state functional connectivity. Age, sex and education will be included as additional regressors.

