Perfusion. PCASL is an arterial spin labeling technique that measures cerebral blood flow. It produces a perfusion image with voxel values representing local perfusion rates. Within FSL we will perform a voxel-wise repeated measures analysis between the pre-LIFUP and post-LIFUP PCASL scans. By examining the differences between these two scans, we can determine the effects that LIFUP has on perfusion in the target region and other connected regions. We will also perform a repeated measures analysis of perfusion between conditions (LIFUP vs. sham). By examining subjects receiving sham on visit 2, we can compare pre-sham resting state fMRI and PCASL to the pre-LIFUP values at visit one, to determine the persistence of blood flow effects over a 2-week interval. This will suggest how frequently LIFUP would need to be administered during a more comprehensive clinical trial.

Motor Assessment. Subjects will undergo a motor evaluation with assessments of motor symptoms such as a grooved pegboard task, a 15-second recording of forearm and hand tremor, and dynamometer grip strength measurements. They will also complete The Essential Tremor Rating Assessment Scale (TETRAS) and the Unified Parkinson's Disease Rating Scale (UPDRS). The motor testing portion of the UPDRS will be video-recorded for research staff to review after the session in order to maximize rating accuracy. Any recordings containing participants faces will be exclusively stored locally on UCLA-owned devices kept in a locked room; any video transferred off these devices will first be edited to remove faces and any other identifying information. The original footage will be deleted once this editing is complete. Participants will complete all of these assessments both before and after the MRI/LIFUP portion of each session. We will also ask the participant's partner or caregiver to complete part 1 of the TETRAS during the first virtual session. In addition to the measurements taken during the in-person and virtual sessions, we will ask participants to wear a watch-style device called the Personal KinetiGraph (PKG) starting one week prior to their first in-person session and ending one week after their second in-person session. This device provides round-the-clock monitoring of tremor activity and sleep quality. Additionally, immediately after administering LIFUP or sham stimulation, we will be asking participants open-ended questions about any perceived changes.

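### The resting-state connectivity effect of LIFUP is judged from before/after change alone, with covariates that cannot protect that contrast; use the sham session and model visit order

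*Combined protocol and SAP*

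**What the plan says.** All places are in the combined protocol and SAP.

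- **APPROACH, Participants:** "Participants will consist of 30 adults, aged 18 to 85 years". No alpha, power or effect size is given.
- **APPROACH, fMRI Validated LIFUP stimulation:** each person has active sonication at one visit and sham at the other, "the order of which will be randomized and counterbalanced across participants".
- **PROCEDURES, RS-fMRI:** "We will compare rs-FC before and after stimulation", then "Dual-regression analysis will then compare resting state networks between baseline and post-LIFUP to determine the effect of LIFUP on resting state functional connectivity", then "Age, sex and education will be included as additional regressors". The group-level model is not given. The paragraph does not say whether it uses person terms or difference maps, or whether covariates are centred. It states no comparison with sham.
- **PROCEDURES, Perfusion:** besides a pre/post analysis, the plan compares perfusion under LIFUP with perfusion under sham by repeated measures. No order, period or sequence term is named, and it is not said whether changes or post-scan values are compared. A further comparison sets pre-sham scans at visit 2 against pre-LIFUP scans at visit 1, for persistence.
- **PROCEDURES, MRI Analysis:** "Subjects with greater than 0.5mm mean framewise displacement will be excluded from analyses".
- **STUDY DESIGN:** active versus sham is the independent variable, and rs-FC is among the dependent variables. Pre- and post-stimulation PCASL and resting-state scans are collected at both in-person sessions.

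**The concern.** A change from before to after sonication in one session mixes any effect of LIFUP with everything else that happens during a scan of about 75 minutes: time in the scanner, drowsiness, habituation. The sham session exists to measure that background change, but the rs-FC paragraph does not subtract it.

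The adjustment the paragraph does specify cannot do this work. Age, sex and education are the same before and after, so they cannot confound the difference.

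The feature that does vary with condition, the visit at which active treatment is given, appears in no stated model. Connectivity is Aim 3 and feeds Aim 4, so the contrast that carries the rs-FC conclusion should be the one the randomisation supports.

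**Working it through.** The plan states no power or effect figure, so there is nothing to reproduce. From the documents: N = 30, two visits, order counterbalanced (hence 15/15 if complete). **Assumed, not in the documents:** two-sided alpha 0.05; true effect 0.53 SD of the analysed difference (about 80% power); age mean 65 (SD 8), education mean 16 (SD 2.5), half of each sex; period effects of 0 to 1 SD; a 14/10 split after exclusions. Simulations used 5,000 runs per setting.

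**1. Covariates alongside person terms.** Thirty person columns plus a pre/post column have rank 31. Adding age, sex and education gives 34 columns, still of rank 31. In a simulated dataset the pre/post estimate (0.395), its SE (0.162) and the error df (29) are the same with and without them. They have no effect on the test.

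**2. Mean-centred covariates in a difference model.** The intercept is the mean change at the sample's average covariates. The noncentrality is 0.53 × √30 = 2.90. Power is 0.801 with 29 df and 0.798 with 26 df. If age explains 10% of the variance in change, simulated power is 0.83 with centred covariates and 0.81 without. Larger gains at higher shares are partly conditional on the sample drawn.

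**3. Uncentred covariates in a difference model (conditional; the plan does not state this coding).** The intercept becomes the change at age 0 with 0 years of education. If the covariates explain none of the change, its SE rises from 0.18 (1/√30) to 2.03–2.05 and power falls from 0.80 to 0.06. If age explains 30% of the variance in change and the true mean change is zero, the test rejects in 71% of runs.

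**4. Visit order in the active-versus-sham contrast.** Let D = (post − pre, active) − (post − pre, sham). Write D = δ + π·o + error, with o = +1 or −1 by order and error SD 1.

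With 15/15, the mean of D is unbiased for δ whether or not o is fitted. Omitting o leaves π in the residual, whose SD becomes about √(1 + π²·30/29): 1.12 at π = 0.5 and 1.43 at π = 1.

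| Period effect π (SD) | Power, order omitted | Power, order included |
|---|---|---|
| 0 | 0.81 | 0.81 |
| 0.25 | 0.78 | 0.80 |
| 0.5 | 0.72 | 0.80 |
| 1 | 0.50 | 0.80 |

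With 14/10, omitting o biases the estimate by π × (14 − 10)/24 = π/6, which is 0.04, 0.08 and 0.17 SD at π = 0.25, 0.5 and 1. Fitting o removes the bias.

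**5. Coding of order.** With +1/−1 coding the intercept is the average effect over both orders. Its noncentrality is 2.90 on 28 df, so power is 0.80. With 0/1 coding the intercept is the effect in one order only, resting on 15 people: 0.53 × √15 = 2.05 on 28 df, power 0.51.

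**The case against.** Four points are fair, and most of them stand.

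*The covariates may do no harm.* This stands. A reader might infer that the three regressors must either do nothing or damage the test, or that they remove most of its power. The documents do not support that. Steps 1 and 2 show two ordinary models in which they are harmless. The severe loss in step 3 needs uncentred coding with the raw intercept read as the effect. A loss from abandoning the pairing would need an unpaired model. The plan states neither, and the neighbouring perfusion analysis is explicitly repeated-measures. The covariate sentence may also be meant partly for Aim 1, where such adjustment is sensible.

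*Order is constant within a person too.* This stands for the before/after contrast in the active session, where order is as redundant with person terms as age is. The case for an order term therefore applies to active versus sham.

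*Counterbalancing already protects against order effects.* It protects against bias while the orders stay balanced. It does not recover precision, and the head-motion exclusion could unbalance the orders.

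*Sham is already part of the design.* STUDY DESIGN does name active versus sham as the independent variable and rs-FC as an outcome. It would go too far to infer that the investigators will ignore sham for rs-FC; the session's baseline scans are already assigned to the persistence question. What is missing is an analysis statement that contrasts change under the two conditions.

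One cost is real. If changes in the two sessions have equal SD and correlation ρ, subtracting sham multiplies the SD by √(2(1 − ρ)): 1.41 at ρ = 0, 1.00 at 0.5, 0.63 at 0.8. The active-only contrast may therefore be more precise, but what it estimates is not the effect of LIFUP net of the session.

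**Conclusion.** The point holds as a gap in the stated analysis, not as a demonstrated error in a fitted model. As written, rs-FC change after LIFUP is attributed to LIFUP without a sham contrast, and the named covariates cannot make up for that. Coding and centring are unstated, so the text permits both a sound test and a badly distorted one.

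The size of the sham omission cannot be computed, because the plan gives no figure for background change within a session. The size of the order omission depends on the period effect: nothing at zero, about 8 percentage points of power at 0.5 SD and 30 at 1 SD with 15/15. Bias appears only with unbalanced orders, at one sixth of the period effect for 14/10. All of this assumes an effect of 0.53 SD at two-sided 5%. The order term does not correct for carry-over between visits, which is a separate question.

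This is a free improvement rather than a fault that invalidates the trial.

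**What to change.** Replace the group-level sentences for rs-FC, and complete those for perfusion, as follows.

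- Compute for each participant the difference image (post minus pre, active session) minus (post minus pre, sham session). Test its mean with visit order as a regressor, effect-coded +1/−1 rather than 0/1, so that the intercept is the average LIFUP effect over both orders.
- Leave age, sex and education out of this contrast or, if they are kept as possible modifiers of the effect, mean-centre them over the participants analysed.
- Keep the three covariates for the between-person associations in Aim 1, and say so.
- Report the active-session before/after comparison, if wanted, as descriptive.

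The cost is one sentence of analysis wording and one degree of freedom (29 to 28 with 30 participants). No new data are needed, since all four scans per person are already scheduled. Group-level analysis is planned only after 30 subjects have been collected, so the model can be fixed before then.

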- During in-person session #2 (two weeks after in-person session #1), we will administer pre-LIFUP behavioral and motor testing, MRI, either LIFUP or sham stimulation (whichever was not received during the first session), and post-LIFUP motor testing.
- 48-72 hours after each in-person session, behavioral testing will be administered, as well as motor testing that can be conducted remotely.
- 4 and 7 days after each in-person session, a brief follow-up call will be conducted.
- Participants will be wearing the PKG device round-the-clock from one week prior to the first in-person session until one week after the second in-person session.
- The independent variable is the type of LIFUP modulation we will perform: active stimulation vs. sham stimulation.
- The dependent variables are: resting-state functional connectivity, perfusion, severity of motor symptoms, severity of psychological symptoms, and performance on the probabilistic learning task.

Detailed Design

Pre-screen: when we are put in contact with a potential participant, we will ask them to undergo a brief screening over the phone. The purpose of this session is exclusively to determine eligibility with respect to the following inclusion and exclusion criteria:

- **Inclusion Criteria:** (i) diagnosis of PD, (ii) age 18-85, (iii) fluent in English, (iv) hearing and vision normal or corrected-to-normal, and (v) willing and able to provide informed consent
- **Exclusion Criteria:** (i) mobility issues requiring use of a wheelchair or walker, (ii) significant cognitive impairment, (iii) history of neurological disorder other than Parkinson's, (iv) history of psychiatric disorders other than sleep disorders, anxiety disorders, and major depressive disorder, (v) pre-PD history of sleep disorders, anxiety disorders, and/or major depressive disorder, (vi) contraindication to MRI, (vii) medication changes within past 6 weeks or planned changes in next 6 weeks, (viii) pregnant or planning to become pregnant, (ix) history of medical event(s) likely to result in neurological abnormalities, (x) uncontrolled diabetes or hypertension, (xi) diagnosis of severe lung, liver, heart, or kidney disease, (xii) history of alcohol or substance abuse (other than nicotine or caffeine)

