The only data that will be retained about this screen is whether the participant is currently eligible, ineligible, or eligible at some future date, as well as their necessary contact information and any information necessary to verify MRI safety. No other record will be kept of the contents of the potential participant's answers.

Remote Session 1 [90 minutes]

The aim of this session is to (a) complete informed consent procedures, (b) evaluate cognitive status via the TICS-M (c) complete MRI safety screening procedures, (d) obtain participant demographic and medication information, (e) have caretaker complete part 1 of the TETRAS, and (f) schedule all other sessions

Remote PKG Setup Session [approx. 10 minutes]

The aim of this session is to (a) obtain a recording of the participant putting on the PKG device to ensure correct setup and (b) familiarize the participant with the usage of the device. Participant faces and voices will be removed from recordings before they are transferred from UCLA-owned devices to the UCLAHealth Box server. The PKG device will be worn from one week prior to the first in-person session to one week after the second in-person session. To collect continuous tremor data, the PKG device is to be worn round-the-clock, except for when participant is swimming, showering, syncing the device weekly, or in a LIFUP/MRI session.

In-Person Session 1 [approx. 4.5 hours]

This session will take place one week after the PKG setup session. The aim of this session is to (a) complete pre-LIFUP motor assessments (UPDRS, TETRAS, 1-minute forearm recording, grip strength and grooved pegboard tasks), (b) complete pre-LIFUP psychological assessments (SSS, STAI, RBDSQ, QUIP-RS, BDI), (c) perform neuronavigation-guided LIFUP or sham stimulation during rsfMRI, (d) collect information on any perceived changes immediately post-LIFUP, (e) collect pre-LIFUP high res T1w, PCASL, and rsfMRI scans and post-LIFUP PCASL and rsfMRI scans, (f) complete post-LIFUP motor assessments (UPDRS part 3, TETRAS part 2, grip strength and grooved pegboard tasks), and (g) complete post-LIFUP psychological assessments (SSS, PCQ).

Post-LIFUP Remote Session 1 [60 minutes]

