This session will take place 48-72 hours after the first in-person session. The aim of this session is to (a) complete post-LIFUP motor assessments that can be administered remotely (UPDRS parts 1, 2, and 4, TETRAS part 1), (b) complete post-LIFUP psychological assessments (SSS, BDI, RBDSQ, STAI-State, probabilistic learning task), and (c) collect information on any perceived changes not covered in the motor and psychological assessments.

In-Person Session 2 [approx. 4 hours]

This session will take place two weeks after the first in-person session. The aim of this session is to (a) complete pre-LIFUP motor assessments (UPDRS, TETRAS, 1-minute forearm recording, grip strength and grooved pegboard tasks), (b) complete pre-LIFUP psychological assessments (SSS, STAI-State, RBDSQ, BDI), (c) perform neuronavigation-guided LIFUP or sham stimulation during rsfMRI, (d) collect information on any perceived changes immediately post-LIFUP, (e) collect pre-LIFUP PCASL and rsfMRI scans and post-LIFUP PCASL and rsfMRI scans, (f) complete post-LIFUP motor assessments (UPDRS part 3, TETRAS part 2, grip strength and grooved pegboard tasks), and (g) complete post-LIFUP psychological assessments (SSS, PCQ).

Post-LIFUP Remote Session 2 [60 minutes]

This session will take place 48-72 hours after the first in-person session. The aim of this session is to (a) complete post-LIFUP motor assessments that can be administered remotely (UPDRS parts 1, 2, and 4, TETRAS part 1), (b) complete post-LIFUP psychological assessments (SSS,

BDI, RBDSQ, STAI-State, probabilistic learning task), and (c) collect information on any perceived changes not covered in the motor and psychological assessments.

Four-day Post-LIFUP Follow-Up Calls [approx. 5 min each]

These calls will take place four days after each in-person session. The aim of these calls is to collect information on any perceived changes since the LIFUP session or the post-LIFUP Zoom session.

One-week Post-LIFUP Follow-Up Call 1 [approx. 10 min]

This call will take place seven days after the first in-person session. The aim of these calls is to (a) collect information on any perceived changes since the LIFUP session or prior follow-up sessions, and (b) walk the participant through the process of syncing the PKG device in order to ensure successful data transfer.

One-week Post-LIFUP Follow-Up Call 2 [approx. 10 min]

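### The LIFUP-versus-sham perfusion comparison in this two-visit crossover states no visit term; adding one costs a single degree of freedom and protects precision if perfusion shifts between visits

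*Combined protocol and SAP*

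**What the plan says.** The section on fMRI-validated LIFUP stimulation (APPROACH) gives every participant both conditions at separate visits, "the order of which will be randomized and counterbalanced across participants". The visits are two weeks apart (Design Overview).

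PCASL is taken before and after stimulation at both visits. For In-Person Session 1 the plan will "collect pre-LIFUP high res T1w, PCASL, and rsfMRI scans and post-LIFUP PCASL and rsfMRI scans"; for In-Person Session 2 it will "collect pre-LIFUP PCASL and rsfMRI scans and post-LIFUP PCASL and rsfMRI scans". That makes four perfusion scans per person. Aim 2 is framed as "PCASL pre- and post- LIFUP to assess up-regulation of BGTC network perfusion".

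The Perfusion paragraph under PROCEDURES first describes a voxel-wise comparison of pre-LIFUP with post-LIFUP scans. It then adds the controlled comparison: "We will also perform a repeated measures analysis of perfusion between conditions (LIFUP vs. sham"). No visit, period or order term is stated there or elsewhere. The only covariates named in the plan are age, sex and education, in the RS-fMRI paragraph. They are constant (or nearly so) over two weeks, so they cannot stand in for visit. The sentence also does not say whether post scans, pre-to-post changes, or condition-by-time on all four scans is tested.

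On timing, "Group level analysis will occur after data from 30 subjects have been collected".

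**The concern.** Randomizing the order ensures that a general difference between first and second visits does not favour either condition. It does not remove that difference from the data. If perfusion, or its change within a session, differs between visits, people who had active first and people who had active second have active-minus-sham differences shifted in opposite directions. A plain paired analysis treats that spread as random error. A model with a visit term takes it out.

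What is at stake is mainly precision in a sample of 30. There is a secondary issue if the analysed orders are unequal. The MRI Analysis paragraph excludes people whose mean framewise displacement exceeds 0.5 mm, and some may drop out. Part of any visit effect would then enter the unadjusted estimate.

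**Working it through.** The plan states no power, alpha, effect size or SD for this comparison, so there is no figure of its own to reproduce.

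**Inputs from the documents:** 30 participants; two visits; one active and one sham visit per person; counterbalanced order.

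**Assumptions:** a 15:15 split (the documents do not give one); two-sided 5% t test on a single voxel or region; a visit effect π between 0 and 0.8 SD.

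**Model.** For person i the active-minus-sham difference is D_i = τ + s_i·π + e_i. Here s_i is +1 if active came first and −1 otherwise, π is visit 1 minus visit 2, and SD(e) = 1. D is built from whichever perfusion quantity is compared.

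**Bias.** Without a visit term the estimate is the mean of D, with expectation τ + π(n1 − n2)/(n1 + n2). At 15:15 the second part is 0.

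**Precision at 15:15 without the term.** The expected sample variance of D is 1 + (30/29)π². The standard error therefore rises by the factor √(1 + (30/29)π²), and the effective sample size is 30 divided by the square of that factor. For π = 0.5: (30/29) × 0.25 = 0.2586, √1.2586 = 1.122, and 30/1.2586 = 23.8. Power and type I error come from numerical integration, with a normal mean and a noncentral chi-square residual sum of squares (29 df, noncentrality 30π²). Power is for τ = 0.53 SD, which has 80% power when the visit term is included (28 df).

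| Assumed visit effect (SD) | SE increase | Effective n | Power | True type I error |
|---|---|---|---|---|
| 0.1 | 0.5% | 29.7 | 79.8% | 4.9% |
| 0.2 | 2.0% | 28.8 | 78.9% | 4.6% |
| 0.3 | 4.6% | 27.4 | 77.5% | 4.1% |
| 0.5 | 12.2% | 23.8 | 72.6% | 2.9% |
| 0.8 | 28.9% | 18.0 | 60.7% | 1.3% |

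With the term, power is 80% and type I error 5% on every row.

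**Cost of the term when there is no visit effect.** Degrees of freedom fall from 29 to 28 and the critical t goes from 2.045 to 2.048. The interval is 2.0484/2.0452 = 1.0016 times as wide, and power goes from 80.1% to 80.0%. On power, the term breaks even at a visit effect of about 0.06 SD.

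**Unequal orders.** At 12:15 the share of the visit effect entering the unadjusted estimate is 3/27 = 11%; at 10:15 it is 5/25 = 20%. A 0.2 SD visit effect then gives a bias of about 0.02 or 0.04 SD, and a 0.5 SD effect about 0.06 or 0.10 SD. Type I error without the term stays at or below 5% in these four cases. Adjusting raises the standard error by 0.6% at 12:15 and 2.1% at 10:15.

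**Post scans or changes.** Let each scan have variance s², with correlation r_w within a visit and r_b between visits (all between-visit correlations taken as equal). The post-scan difference has variance 2s²(1 − r_b), and the difference of changes has variance 4s²(1 − r_w). The ratio of change to post is 0.4/0.6 = 0.67 at r_w/r_b = 0.9/0.7, 0.8/0.6 = 1.33 at 0.8/0.7, and 1.2/0.6 = 2.0 at 0.7/0.7. Where post scans have 80% power, changes would have about 93%, 68% or 51%. The documents give none of these correlations.

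**The case against.** The strongest reply is that the harm is small and in the safe direction. With counterbalanced order there is no bias, the test errs towards too few false positives, and up to 0.2 SD the loss is about one point of power. Nothing in the documents shows that perfusion differs by visit, and scanner time is alike at both: "Total time in the scanner will be approximately 75 minutes each session". If changes are compared, a shift common to the pre and post scans cancels, and only a visit effect on the within-session change is left. All of this stands, and it is why the point is optional.

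It can also be said that a repeated-measures analysis does not exclude a visit factor and that this is a short outline. That is fair: the text is silent and does not commit to a condition-only model. But the phrase implies only within-person pairing, and a plain paired contrast would satisfy it.

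Three stronger readings are tempting and are not supported:

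- **That the comparison is biased.** With equal orders it is not. With moderately unequal orders only a fraction of a visit effect of unknown size enters.
- **That any visit effect would cost precision.** Below about 0.06 SD the unadjusted test has very slightly more power, and a stable shift cancels if changes are compared.
- **That change scores should be used because they are more precise.** They may gain or lose. At a variance ratio of 1.33 the standard error rises by 15%, which is more than omitting the visit term costs at a 0.5 SD visit effect.

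**Conclusion.** The point holds as an optional, low-cost improvement. The trial randomizes order, but its only written LIFUP-versus-sham outcome analysis states no term for it. The possible loss runs from negligible (0.1 SD or less) through about 7 points of power at 0.5 SD to about 19 points at 0.8 SD, against 0.1 point if the term proves unnecessary. The visit effects are assumed, so the documents support saying that the term is unstated and cheap, not that precision is actually being lost.

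The figures rest on 30 analysed people at 15:15. Power and type I error are for a single test, not a corrected voxel-wise threshold; the standard-error figures apply to each voxel or region. The visit term does not deal with carryover, which the Perfusion paragraph itself treats as possible when it looks for persistence of blood-flow effects over the two-week interval.

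**What to change.** In the Perfusion paragraph, state that the LIFUP-versus-sham comparison includes visit (1 or 2) as a within-person term. Equivalently, regress each person's active-minus-sham difference on order coded +1/−1 and not mean-centred. The intercept is then the average of the two order-specific means, even when the orders are unequal.

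Use the same term in any active-versus-sham comparison of the other dependent variables, which include "severity of psychological symptoms, and performance on the probabilistic learning task". The learning task is given only at the follow-up sessions, so it has no pre-stimulation score that could absorb a visit shift.

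Also name in advance which perfusion quantity is tested: post scans, pre-to-post changes, or condition-by-time on all four scans. That choice should follow the aim and, if precision is the argument, evidence on the within-visit and between-visit correlations.

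The cost is analysis wording and one degree of freedom. Visit order is fixed by the design, and no new data are needed.
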